1. INTRODUCTION

1.1. BACKGROUND

1.1.1. Scientific Background and Clinical Rationale

Obesity, a major health concern today, is a direct result of food-intake in excess of body energy expenditure. However, there is a vast amount of published information that proves that for some people, obesity is not the result of excessive food consumption, poor food choices, and failure to exercise (1). Problems with mitochondria, leaky lymphatics and other mutations can drive and maintain fat growth that cannot be lost through traditional diet and exercise (2). Dercum's Disease (Adiposis Dolorosa), Madelung's Disease, lipedema and Familial Multiple Lipomatosis or Angiolipomatosis are names of some of such fat disorders. These are known as Rare Adipose Disorders; they are painful, progressive disorders that result in abnormal accumulations of fat in the form of lipomas, excess lymphatic fluid, and many other symptoms.

Lipedema is a chronic condition, initially described in 1940, that occurs almost exclusively in women and manifests as symmetrical buildup of painful fat and swelling in the limbs, sparing the hands and feet (3). Fat tissue expands primarily in the lower limbs, from buttocks to ankles, as well as in the arms. Upon palpation of the fat, tiny pebbles or pea like nodules are felt. As the disease advances the nodules may increase in size and in number and may form strands of nodules(4). There are no diagnostic tools or tests for lipedema. Diagnosis of lipedema involves a clinical assessment and discussion of the individual's medical history, a process that is difficult to scale within the current healthcare system. The absence of diagnostic tools to streamline or confirm a clinical diagnosis is a key unmet need, which if addressed, has the potential to dramatically change the trajectory of the disease (5). Individuals who suffer from the disease are further impacted by the lack of public and medical awareness of lipedema, and the stigma associated with weight gain. As a result, the epidemiology of lipedema is unknown (6).

The etiology of lipedema and other types of fatty tissue enlargement is still unknown, though a genetic cause is suspected. Other possible causes of lipedema include metabolic, inflammatory, or hormonal involvement. Although the disease is reported to occur during puberty and other periods of hormonal changes, why this happens is not understood.

Lipedema is sometimes accompanied by co-morbidities, often secondary diseases, which complicate the patient's health. Psychosocial issues are prevalent in women with lipedema, contributing to health burden and complexity of disease management. The painful fat and swelling in some patients can be so debilitating that their mobility is impaired. Furthermore, many patients develop the disease alongside obesity; however, diet, exercise, and weight loss surgery have limited effect on lipedema fat.

A critical issue is the poorly understood disease, which for diagnosed patients results in limited treatment options that, at best, ameliorate the symptoms of lipedema. Early detection and treatment can significantly reduce the debilitation of the patient. Early weight and diet changes

through nutrition and exercise may be helpful in reducing non-lipedemic fat and reducing inflammation. This approach may possibly prevent the lower body from enlarging as much as it would if the patient were to become obese. However, even with strict diet and exercise regimens the disease may progress and further treatments may be necessary. While there is no proven effective treatment for lipedema, the swelling may be somewhat managed with compression garments, manual lymphatic drainage and/or Complete Decongestive Therapy. Unfortunately, some products such as garments may not be well tolerated by all patients if the patient experiences pain. Liposuction as a treatment for lipedema was developed in Germany in the late 1980s and is becoming more common. However, given the fact that liposuction is a surgery, it is not a risk-free procedure. While it has helped some patients when done by a skilled surgeon knowledgeable about lipedema, very few physicians in the United States have the knowledge and experience of physicians in Europe. Currently, different liposuction procedures (Water Assisted Liposuction [WAL] and Tumescent Liposuction [TLA]) used for lipedema patients are available but not all surgeries are suitable for all patients (7).

Dercum's disease was first described in the medical literature in 1882 by an American neurologist named Francis Xavier Dercum's. Dercum's disease is an extremely rare disorder (listed by NORD [National Organization for Rare Disorders]) characterized by multiple, painful growths consisting of fatty tissue (lipomas). These growths mainly occur on the trunk, the upper arms and upper legs and are subcutaneous. Pain associated with Dercum's disease can often be severe. Pain may be caused by these growths pressing on nearby nerves. Some individuals with Dercum's may experience swelling of various areas of the body, especially the hands. Swelling occurs for no apparent reason and often disappears without treatment. In some cases, affected individuals may also experience weight gain, depression, lethargy, and/or confusion.

The etiology of Dercum's disease is unknown, though a genetic cause is suspected (autosomal dominant). Other possible causes playing a role in the development of Dercum's disease include autoimmune disorder, disturbances in endocrine function, improper metabolism of fat and the use of high-doses of corticosteroids.

The prevalence of Dercum's disease is unknown. Dercum's disease affects females more often than males with some reports citing the disease is as 20 times more common in women. Dercum's disease can affect individuals of any age. The majority of cases are women between the ages of 45-60, especially overweight, postmenopausal women.

No specific treatment exists for Dercum's disease. Treatment is mainly symptomatic and supportive and is primarily focused on easing the characteristic painful episodes. Various analgesics have been tried with limited effectiveness. Surgical excision of fatty tissue deposits around joints may temporarily relieve symptoms although recurrences often develop. Liposuction has been used as a supportive treatment for some individuals with Dercum's disease and may provide an initial reduction in pain and improvement in quality of life (QOL) (8). These effects may lessen over time. Psychotherapy and consultation with pain management specialists may be helpful for enabling affected individuals to cope with long-term intense pain.

RZL-012 is a novel synthetic molecule enabling the conversion of white adipose tissue (WAT) into an activated thermogenic tissue at targeted anatomical sites. A single injection of RZL-012 into WAT is sufficient to trigger robust tissue remodeling. A chain of events begins with removal of WAT adipocytes by macrophages (liponecrosis), followed by an activation of remodeled cells that generate a futile cycle of ongoing energy conversion into heat. Temperature measurements of the site treated by RZL-012 reveal a persistent local increase in temperature (about 4 months in pigs). As long as these cells are active, the ensuing thermogenic tissue will consume free fatty acids (FFA) from the nearby surrounding adipose depots and further from glucose and FFA supplied via the blood stream.

The overall clinical plan for RZL-012 includes the completed exploratory (phase 0) study to evaluate the safety, thermogenesis, and pharmacodynamic response to RZL-012. An additional phase 2 study ([Study RZL-012-P2aUS-001.1](#)) in overweight and obese subjects to confirm the safety and pharmacodynamic effects of RZL-012 for the treatment of obesity will be initiated soon to explore the response to higher doses prior to the initiation of larger studies. The initial exploratory study ([Study RZL-012-P0US-001.3](#)) demonstrated that RZL-012 is well tolerated with no serious adverse events reported and that thermogenesis was evident at the injection site (abdomen) of RZL-012-treated obese subjects. Although not statistically significant (due to the initially tested low dose and a small-size study group, n=6), there was a decrease in subcutaneous fat mass (SFM) over time (compared to baseline) in the abdomen, as measured by Magnetic Resonance Imaging (MRI), in 5 out of 6 RZL-012 treated subjects, but none in vehicle treated ones.

Raziel Therapeutics believes that RZL-012 effects of adipose-tissue replacement thermogenic tissue and the ongoing lipolysis and consumption of FFA from nearby adipose tissue by the remodeled cells can be beneficial to patients with fat disorders such as lipedema and Dercum's disease. Local fat reduction and tissue remodeling at selected sites such as at the medial knee in lipedema patients and at lipomas in Dercum's disease patients may bring pain relief and improvement in QOL.

The current Phase 2a study is aimed to evaluate the safety and pharmacodynamics response to RZL-012 in lipedema and Dercum's disease patients.

1.1.2. RZL-012 Formulation Development

The active ingredient RZL-012 drug substance was manufactured by Pharmcore, High Point NC, USA. The drug product, 5 % RZL-012 in F12 liquid formulation (RZL-012 in F12 is 5 g/vial, RZL-012 is 250 mg/vial) was manufactured and packed at Nextar Ltd, Ness-Ziona, Israel. RZL-012 in F12, which was once defined as RZL-012 F12, is now defined as RZL-012. The active ingredient and formulation manufacturing and packing were in accordance with current Good Manufacturing Practices (cGMPs).

1.2. NONCLINICAL ASSESSMENTS

1.2.1. Pharmacology

Studies in rats and pigs concluded that RZL-012 triggers remodeling of WAT to brown-like adipose tissue (BAT) tissue, thereby activating thermogenesis. The dose of RZL-012 to be used in clinical trials was extrapolated from the safety data obtained during animal testing no observed adverse effect level (NOAEL).

1.2.1.1. Efficacy In-vivo and In-vitro Studies

Nonclinical studies were conducted to prove the efficacy of RZL-012 in several in-vivo and in-vitro models.

The in vivo studies (in pigs and rats) involving local administration of RZL-012, focused on two main endpoints: fat tissue reduction and conversion of WAT to BAT, measured by several parameters, including;

1. Subcutaneous or epididymal fat reduction following RZL-012 treatment.
2. Fat tissue remodeling involving non-inflammatory liponecrosis, followed by tissue "browning", where WAT is converted to BAT in rodents and smooth-muscle-like tissue in larger mammals. This conversion can be determined by:
 - a. *Histological fat tissue changes*: While white adipocytes are large and resemble a single large oil drop, with a characteristic condensed nucleus, the cells of BAT are smaller, contain multiple mitochondria and a euchromatic nucleus.
 - b. *Uncoupling protein 1(UCP-1) levels*: UCP-1 is a mitochondrial inner membrane protein present in BAT that can dissipate the proton gradient before it can be used to provide the energy for oxidative phosphorylation. UCP-1 normally does not exist in WAT.
 - c. *Smooth-muscle-like thermogenic tissue*: In pigs, examination of tissue-sections taken from the site of injection, where robust thermogenesis was observed, revealed smooth-muscle-like histology, including typical molecular markers such as α SMA.
3. Assessment of body-surface temperature: Thermogenic tissue, e.g. classical BAT, is typified by futile burning of fatty acids (i.e., heat production instead of adenosine triphosphate [ATP]), which can be assessed utilizing infrared camera that can measure differences in body surface temperature.

The objective of the in-vitro studies was to reveal the mechanism of action of RZL-012 in adipocytes. Studies were conducted on the 3T3-L1 adipocytes line, which is considered a model for WAT.

1.2.1.2. Safety Pharmacology

The effect of RZL-012 on the central and peripheral nervous systems was evaluated using the Functional Observational Battery (FOB) in male Sprague Dawley rats. RZL-012 was administered subcutaneously to rats (n = 8/group) as 10 mg/rat. From the results, it was concluded that RZL-012 did not affect any of the central nervous system (CNS) functions tested using FOB in rats.

The effect of RZL-012 was evaluated on respiratory functions in male Sprague Dawley rats using head-out plethysmography. RZL-012 was administered subcutaneously at a fixed dose of 10 recorded to cover the entire predetermined time points: Pre-dose, 1, 2, 3, and 4 h post dose. RZL-012 did not affect any of the parameters tested; hence it was concluded that RZL-012 has no effects on the respiratory system at the tested dose of 10 mg/rat.

A board-certified veterinary cardiologist conducted a qualitative and quantitative review of the electrocardiograms (ECGs) obtained pretest, pre-dose, 4 and 24 hours post-dose following the subcutaneous injection of 500 mg 5.0 % RZL-012 or vehicle in Domestic Yorkshire Crossbred Swine. There was no effect of the subcutaneous injection of 5.0 % RZL-012 on qualitative or quantitative ECG parameters or blood pressure.

1.2.2. Toxicology

The study design was to evaluate the safety of RZL-012 according to Food and Drug Administration (FDA) guidelines for Exploratory Investigational New Drug (IND) appropriate for first-in-man clinical trial. An extended single-dose toxicity study was performed according to FDA guidance in two species (rat and pig) to establish the NOAEL.

1.2.2.1. Extended Single Dose Toxicity Studies

1.2.2.1.1. Rats

Single subcutaneous administration of test item RZL-012 at the doses of 5, 10, and 20 mg/kg in Sprague-Dawley rats resulted in non-systemic effects and or local effects at the treated skin area. Few changes observed in haematological parameters (white blood cells [WBC] count, neutrophils, monocytes and eosinophils) were considered secondary effects due to inflammatory response (local skin reactions). The changes observed in clinical chemistry parameters (increased blood urea nitrogen [BUN] in males and females and increased creatinine and aspartate aminotransferase [AST] levels in females) at all the doses tested and histopathological changes in kidneys (necrosis in tubular epithelium) at 20 mg/kg were considered systemic effects. Methods and results from the extended single dose toxicity study are described in the Investigator's Brochure (IB).

Considering skin changes as non-systemic effects and or local effects, the NOAEL was determined at 5 mg/rat with an average body weight of 258.9 g, under the test conditions and doses employed.

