3.2. DOSE RATIONALE

The initial dose was determined by the NOAEL established by the Good Laboratory Practice (GLP) extended single dose toxicology study and by the previous phase 0 clinical trial in which 20mg RZL-012 was the highest dose achieved. This initial study is an escalating dose study. If no more than 1 subject experiences intolerable side effects within 14 days following the injection of the last dosed group, according to schedule, an additional cohort of volunteers will be administrated the next dose level.

Cohort 1- will be comprised of subjects with Dercum's disease. All subjects will be injected with RZL-012. Dosing will be calculated according to the size of the nodule (diameter) as determined by ultrasound: 5mg/cm² reaching a maximal dose of 40 mg RZL-012 per subject (1/6.25 the NOAEL based on the Human Dose Equivalent [HED] GLP Toxicology studies).

Cohort 2 - will be comprised of subjects with lipedema with substantial fat above the knee and will be conducted in a dose escalation manner.

The first 3 subjects will receive 60mg RZL-012 (1/4.688th the NOAEL based on HED from GLP toxicology study).

The last 3 subjects will receive 80mg RZL-012 (1/3.125th the NOAEL based on HED from GLP toxicology study).

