7.2. SAFETY MEASUREMENTS

Simple measures may help avoid specific AEs associated with the use of the RZL-012 investigational product. Thus, study subjects must be informed of possible AEs that occurred in animal studies (rats and pigs):

- Any injection site reaction may occur. Pain, swelling, itching, edema, erythema, hematoma, etc.
- Slight transient injection site bleeding following injection may occur.
- Itching in the injected area may occur, and study subjects should be advised to use an antihistamine gel for topical use according to drug recommendations, wear wide cotton shirts, prevent touch with irritable clothing, avoid scratching and avoid exposure to direct sun. Itching is expected till 7 days following drug injection.
- Local erythema in the injected area.
- Local heat in the injection area.
- Study restrictions regarding concomitant medications are listed in Section 7.1.
- The local subcutaneous fat reduction may appear as a slight dip in the skin surface. This decline may be temporary and transient.

- Transient increase (72%) in the WBC count by 24 hours following injection, which returned to basal level after 14 days. Probably associated with the inflammatory response at the site of injection and involve neutrophils, monocytes and eosinophils.
- Increased level of BUN and of creatinine and minimal single cell necrosis was observed in tubular epithelium at cortico medullary junction of kidney in rats receiving a dose 25 times the highest dose in this study. All abnormalities were found to be reversible by Day 14.
- Increased AST level which is most typical of myofiber injury associated with study related procedures. This elevation was found to be reversible by Day 14.
- Transient increase of serum CRP levels (in rats) which returned to the basic level by 14 days.
- Marked irritancy in the injected subcutaneous tissue resulting in coagulation necrosis of relatively large areas in the subcutaneous tissue planes acutely. Necrosis persisted for up to 14 days and was accompanied by early evidence of healing in the form of chronic inflammation and fibrosis.
- Local inflammation (minimal to moderate) with muscle degeneration, epidermal/dermal necrosis (minimal to severe) and parakeratosis (minimal). Inflammation observed at injection site was also extended to adjacent subcutaneous adipose tissue (SAT). By 56 days the inflammation was minimal, muscle degeneration was not evident and inflammation to adjacent SAT was present.

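### The statement that rat kidney findings occurred at 25 times the study's highest dose conflicts with the Protocol's own rat data and does not fit the 80 mg level

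*Protocol*

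**What the plan says.** Protocol section 1.2.2.1.1 (Rats) describes single subcutaneous dosing "at the doses of 5, 10, and 20 mg/kg in Sprague-Dawley rats". It says that rises in BUN in both sexes, and in creatinine and AST in females, "at all the doses tested and histopathological changes in kidneys (necrosis in tubular epithelium) at 20 mg/kg were considered systemic effects". The NOAEL is then set with one stated qualification, "Considering skin changes as non-systemic effects and or local effects", and the result is that "the NOAEL was determined at 5 mg/rat with an average body weight of 258.9 g". For methods and results the section points to the Investigator's Brochure.

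Protocol section 7.2 lists the animal findings of which subjects must be informed. One bullet groups raised BUN, raised creatinine and minimal tubular necrosis, places them "in rats receiving a dose 25 times the highest dose in this study", and says that they had reversed by Day 14. A separate bullet describes a rise in AST as typical of muscle-fibre injury from study procedures, also reversible by Day 14. That bullet names no dose multiple and no species.

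Protocol section 3.2 gives the dose scale: "The last 3 subjects will receive 80mg RZL-012 (1/3.125th the NOAEL based on HED from GLP toxicology study". It puts the 40 mg maximum of Cohort 1 at 1/6.25 of the same NOAEL. SAP section 5.2 repeats both fractions.

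**The concern.** The multiple in section 7.2 is the only figure in that list that tells a subject or an investigator how far this study's doses lie from the rat kidney findings. It is attached to three findings at once. The rat section confines only one of them, the necrosis, to the top dose and reports the other two at every dose. The multiple also has to agree with the NOAEL fractions in section 3.2, because both express rat findings relative to the human dose.

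If the figure is wrong or mixes findings, the changes in renal markers are presented as more remote than the Protocol's own toxicology summary supports. Two further points in the rat section stand in the way of a clean correction: the dose unit is inconsistent, and the text does not explain how the NOAEL was reached despite chemistry changes that it classes as systemic.

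**Working it through.** **Inputs**
- Rat doses: 5, 10 and 20, printed as mg/kg (1.2.2.1.1).
- BUN and creatinine rises: every dose. Tubular necrosis: 20 mg/kg (1.2.2.1.1).
- Rat NOAEL: 5 mg/rat at 258.9 g (1.2.2.1.1).
- Highest study dose: 80 mg, at 1/3.125 of the NOAEL; 40 mg is at 1/6.25 (3.2).
- Stated multiple: 25 times the highest study dose (7.2).

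**Step 1. One multiple for three findings.** Top rat dose / lowest rat dose = 20/5 = 4, whichever unit is meant. If 25 times is the top dose, the lowest dose with chemistry changes is 25/4 = 6.25 times on the same scale. This step needs no NOAEL, no species scaling and no body weight.

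**Step 2. The human NOAEL implied by section 3.2.** Dose x denominator: 80 x 3.125 = 250 mg, and 40 x 6.25 = 250 mg.

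**Step 3. The unit of the rat NOAEL.** 5 mg / 0.2589 kg = 19.3 mg/kg. Against doses printed in mg/kg, that is about the top dose, not the lowest. It equals the lowest dose only if the printed mg/kg is a slip for mg/rat. Section 1.2.1.2 does give rat doses in mg/rat in other studies, which makes a slip plausible but does not establish it.

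**Step 4. Can 25 times be reproduced?** Multiple = 250 mg x (rat dose / rat NOAEL) / study dose. The assumption is that the 250 mg scales from the rat NOAEL, the only NOAEL for which the documents give a value.

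| Reading of rat doses | Rat dose | Human equivalent | Multiple of 80 mg |
|---|---|---|---|
| mg/rat | top, 20 | 250 x 20/5 = 1000 mg | 12.5 |
| mg/rat | lowest, 5 | 250 mg | 3.125 |
| mg/kg as printed | top, 20 | 250 x 20/19.3 = 259 mg | 3.2 |
| mg/kg as printed | lowest, 5 | 250 x 5/19.3 = 65 mg | 0.8 |

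For 25 times 80 mg the rat dose would have to correspond to 25 x 80 = 2000 mg, or 2000/250 = 8 times the NOAEL. Neither reading gives that.

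**Step 5. Where 25 does come out.**
- Against a 40 mg maximum, with rat doses in mg/rat: 1000/40 = 25.
- Against 80 mg with no species scaling, for the top dose in mg/kg and an assumed 100 kg person: 20 / (80/100) = 25. At 80 kg the same comparison gives 20, and at 60 kg it gives 15.

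Both are routes to the top rat dose. Neither gives 25 for the lowest dose at which BUN and creatinine rose.

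**Step 6. AST.** Section 1.2.2.1.1 counts the AST rise among the systemic effects, whereas section 7.2 attributes an AST rise to procedures. Section 1.2.4 cites the AST rise in female rats, next to a transaminase elevation in a Phase 0 subject, as a reason for close liver monitoring.

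**The case against.** The strongest reply is that section 7.2 does not state its scale. An unscaled mg/kg comparison in a heavy subject gives 25, so the figure may be correct on a basis that is not written down. That stands, and it rules out saying that 25 can only be left over from a 40 mg maximum. It does not help with the chemistry changes, because on that same basis they start at 6.25 times. It would also mean that section 7.2 uses a different scale from section 3.2 without saying so.

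Second, the bullet can be read as describing the animals in which all three findings occurred together. On necrosis alone, sections 1.2.2.1.1 and 7.2 do agree that it is a high-dose finding, and only the multiple is in doubt. For BUN and creatinine this reading leaves section 7.2 silent about the lower doses at which they also rose.

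Third, a reader might infer that the NOAEL is invalid because it sits at a dose with systemic effects. The documents do not support that. Changes judged non-adverse can occur at a NOAEL, section 7.2 reports that the kidney findings reversed, and the details are in the Investigator's Brochure, which was not available. What can be said is that the Protocol sets aside only the skin changes and leaves this step unexplained. Nor can it be said that the NOAEL is the lowest rat dose, given the units in Step 3.

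Fourth, section 3.2 does not name the species behind its NOAEL. Section 1.2.2 says that two species were used, and the pig study is described as GLP with no clinical chemistry changes attributed to the test article. A pig basis for the 250 mg is therefore possible. The multiples in Step 4 depend on the rat assumption; Step 1 does not.

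Finally, a reader might infer that the margin to a liver-marker change is also misstated. Section 7.2 gives no multiple for AST. Because its AST bullet names no species, it may refer to a different study from the rat summary. The attribution needs to be aligned, but no margin has been shown to be wrong.

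**Conclusion.** The point holds. Section 7.2 ties the BUN and creatinine rises to a single multiple of 25, while section 1.2.2.1.1 reports them across a 4-fold dose range; on the same scale they begin at no more than 6.25 times if 25 is the top dose. This rests only on the two sections' own text.

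The multiple also fails to fit the 80 mg level on the NOAEL scale of section 3.2. The top rat dose is 12.5 times 80 mg if rat doses are in mg/rat and about 3.2 times if they are in mg/kg as printed, assuming that the 250 mg derives from the rat NOAEL. Because the unit, the species and the scale are all unstated or inconsistent, no single factor of overstatement can be given.

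The unit conflict in the rat section, the unexplained NOAEL step and the two descriptions of AST are secondary defects that have to be resolved in the same correction. What subjects actually read is not known, since the consent pages are not in the documents. Whether any dose is appropriate is outside this point.

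**What to change.** Reconcile Protocol sections 1.2.2.1.1, 3.2 and 7.2 from the toxicology reports:
- In 1.2.2.1.1, state one unit for the rat doses and the NOAEL, the doses at which BUN, creatinine and AST rose, and whether these rises were judged adverse and why.
- In 3.2, name the species and study behind the NOAEL and its human equivalent. SAP section 5.2 repeats the fractions and should follow.
- In 7.2, restate the multiple for the 80 mg level with its scaling basis, giving one figure for the lowest dose with chemistry changes and another for the necrosis.
- Align the AST attribution between 1.2.2.1.1 and 7.2, naming the species, and check any consent wording that repeats the multiple.

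The cost is a text amendment, plus a consent revision if the figure appears there. It adds no subjects, visits or analyses, and no dose or clinical rule is proposed.
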